5.5.4. Modified Observer's Assessment of Alertness/Sedation (MOAA/S)

The Modified Observer's Assessment of Alertness/Sedation (MOAA/S) will be used to measure treatment-emergent sedation with correlation to levels of sedation defined by the American Society of Anesthesiologists (ASA) continuum. The MOAA/S scores range from 0 (No response to painful stimulus; corresponds to ASA continuum for general anesthesia) to 5 (Readily responds to name spoken in normal tone [awake]; corresponds to ASA continuum for minimal sedation).

The MOAA/S is measured on each dosing day every 15 minutes from predose to 1.5 hours postdose or longer, if necessary, until the subject has a score of 5 during each induction phase (DB and OL).

- If the score is ≤ 3 at any time during the 1.5 hour postdose interval, the MOAA/S will be performed every 5 minutes until a score of 4 is reached (at which point a frequency of every 15 minutes can be resumed until $t=+1.5$ hours postdose).
- If a subject does not have a score of 5 at $t=+1.5$ hours postdose, they should continue to be monitored. For subjects with a score of 4, the assessment should be repeated every 15 minutes. For subjects with a score of ≤ 3 , the assessment should be repeated every 5 minutes until the score returns to 5 or the subject is referred for appropriate medical care, if clinically indicated.

Descriptive statistics (N, mean, median, minimum, and maximum) of the MOAA/S score, changes from predose, and the proportion of subjects experiencing sedation (score less than or equal to 3) will be summarized at each time point. The proportion of subjects with a total score of 3 or less will be summarized at any time during the study and by dose day. Mean (SE) MOAA/S values will be presented graphically for each dosing day.

5.5.5. Clinical Global Assessment of Discharge Readiness (CGADR)

The Clinical Global Assessment of Discharge Readiness (CGADR) will be used to measure a subject's current clinical status and is the clinician's assessment of the readiness to be discharged from the study site.

The clinician will answer “Yes” or “No” to the question “Is the subject considered ready to be discharged based on their overall clinical status (eg, sedation, blood pressure, and other adverse events)?”

On each intranasal dosing day, the CGADR will be performed at 1 hour and 1.5 hours postdose, repeated every 15 minutes if necessary until the response is ‘Yes’. A subject should not be discharged prior to the 1.5-hour time point.

The proportion of subjects with a response of ‘No’ at each time point will be presented by treatment group during each induction phase (DB and OL).

5.5.6. Physician Withdrawal Checklist (PWC-20)

The PWC-20 is a 20-item simple and accurate method to assess potential withdrawal symptoms following cessation of intranasal esketamine treatment. The PWC-20 will be performed for all subjects on Day 25 DB and Day 25 OL to establish a baseline prior to discontinuation of esketamine treatment.

The proportion of subjects with withdrawal symptoms at the end of induction phases (DB and OL) or during the DB follow-up phase, PT phase and the OL follow-up phase will be presented. In addition, symptoms at PT phase and follow-up phases will be compared to the last assessment in the relevant induction phase (DB and OL) and will be summarized using the following categories: new or worsened symptoms, symptoms present and unchanged, no symptoms, and improved.

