2. OBJECTIVES AND HYPOTHESIS

2.1. Objectives

Primary Objective

The primary objective of the study is to evaluate the efficacy of fixed dosed intranasal esketamine compared to intranasal placebo, as an add-on to an oral antidepressant in Japanese subjects with TRD, in improving depressive symptoms.

Secondary Objectives

- To assess the effect of intranasal esketamine compared with intranasal placebo as an add-on to an oral antidepressant in Japanese subjects with TRD, including the following parameters:
 - Dose response;
 - Depression response rates;
 - Depression remission rates;
 - Onset of clinical response;
 - Overall severity of depressive illness;
 - Anxiety symptoms;
 - Functioning and associated disability.
- To investigate the safety and tolerability of intranasal esketamine compared with intranasal placebo as an add-on to an oral antidepressant in Japanese subjects with TRD, including the following parameters:
 - TEAEs, including AEs of special interest;
 - Potential withdrawal or rebound symptoms or both following cessation of intranasal esketamine treatment;
 - Perceptual changes (dissociative symptoms);
 - Effects on alertness and sedation;
 - Effects on heart rate, blood pressure, respiratory rate, and blood oxygen saturation;
 - Potential effects on suicidal ideation/behavior;
 - Potential abuse-liability;
 - Potential psychosislike effects.
- To evaluate the durability of intranasal esketamine as an add-on to an oral antidepressant in Japanese subjects with TRD, with attention to:
 - Time to relapse in the posttreatment phase for subjects in remission and for subjects who respond but are not in remission, at the end of the double-blind induction phase.
- To evaluate the PK of intranasally administered esketamine in Japanese subjects with TRD.

Exploratory Objectives

- To assess the comparability of the efficacy and safety of intranasal esketamine as an add-on to an oral antidepressant between the double-blind and OL intranasal esketamine induction treatment courses;
- To evaluate the PK/PD relationship of intranasal esketamine and MADRS total score (and possibly selected AEs as additional PD parameters) in Japanese subjects with TRD;
- To examine the relationship between deoxyribonucleic acid (DNA) single nucleotide polymorphisms (SNPs) (including, but not limited to BDNF) with clinical outcome to intranasal esketamine in Japanese subjects with TRD;

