1.1. Trial Objectives

Primary Objective

The primary objective of the study is to evaluate the efficacy of fixed dosed intranasal esketamine compared to intranasal placebo, as an add-on to an oral antidepressant in Japanese subjects with treatment-resistant depression (TRD), in improving depressive symptoms.

Secondary Objective

- To assess the effect of intranasal esketamine compared with intranasal placebo as an add-on to an oral antidepressant in Japanese subjects with TRD, including the following parameters:
 - Dose response;
 - Depression response rates;
 - Depression remission rates;
 - Onset of clinical response;
 - Overall severity of depressive illness;
 - Anxiety symptoms;
 - Functioning and associated disability.
- To investigate the safety and tolerability of intranasal esketamine compared with intranasal placebo as an add-on to an oral antidepressant in Japanese subjects with TRD, including the following parameters:
 - TEAEs, including AEs of special interest;
 - Potential withdrawal or rebound symptoms or both following cessation of intranasal esketamine treatment;
 - Perceptual changes (dissociative symptoms);
 - Effects on alertness and sedation;
 - Effects on heart rate, blood pressure, respiratory rate, and blood oxygen saturation;
 - Potential effects on suicidal ideation/behavior;
 - Potential abuse-liability;
 - Potential psychosis-like effects.

- To evaluate the durability of intranasal esketamine as an add-on to an oral antidepressant in Japanese subjects with TRD, with attention to:
 - Time to relapse in the posttreatment phase for subjects in remission and for subjects who respond but are not in remission, at the end of the double-blind induction phase.
- To evaluate the PK of intranasally administered esketamine in Japanese subjects with TRD

Exploratory Objective

- To assess the comparability of the efficacy and safety of intranasal esketamine as an add-on to an oral antidepressant between the double-blind and open-label intranasal esketamine induction treatment courses;
- To evaluate the PK/PD relationship of intranasal esketamine and MADRS total score (and possibly selected AEs as additional PD parameters) in Japanese subjects with TRD;
- To examine the relationship between deoxyribonucleic acid (DNA) single nucleotide polymorphisms (SNPs) (including, but not limited to BDNF) with clinical outcome to intranasal esketamine in Japanese subjects with TRD;

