2. GENERAL ANALYSIS DEFINITIONS

2.1. Analysis Phases

There are 5 analysis phases defined in this study:

- *A Double-blind Induction Phase*
- *A Double-blind Follow-up Phase* (Non-Responders or subjects who withdraw from DB induction phase)
- *A Posttreatment Phase* (Responders only)
- *An Open-Label Induction Phase* (Responders only)
- *An Open-Label Follow-up Phase* (Responders only)

Each analysis phase has its own analysis phase start and end dates.

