2.4.3. Safety Analysis Set

The following safety analysis sets are defined for each phase. Analyses of change from baseline will include only those subjects who have baseline and at least 1 postbaseline observation in that phase.

Safety (DB): All randomized subjects who receive at least 1 dose of intranasal study medication in the DB induction phase.

Safety (OL): All subjects who receive at least 1 dose of intranasal study medication in the OL induction phase.

Safety (responders): All randomized subjects who receive at least 1 dose of intranasal study medication during the double-blind induction phase and who are responders at the end of the double-blind induction phase and entered the posttreatment phase.

Screen failures and randomized subjects who received no study medication will be excluded from the safety analysis set. Subjects who received an incorrect treatment will be analyzed under the planned treatment.

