2.4.4. Follow-up Analysis Set

The following FU analysis sets are defined for each phase and will be used for both safety and efficacy analyses.

- FU (DB): All subjects who do not respond at the end of DB induction phase and enter the DB follow-up phase
- FU (OL): All Safety (OL) subjects who enter the OL follow-up phase

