5. SAFETY

All safety summaries for induction phases will be based on the safety analysis sets described in Section 2.4.3. Safety summaries for the follow-up phases will be based on the follow-up analysis sets described in Section 2.4.4.

Unless specified otherwise, Baseline (DB) will be used for DB induction phase and DB follow-up phase. Baseline (OL) will be used for OL induction phase and OL follow-up phase.

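### Withdrawal and rebound over the four weeks after stopping are summarised only within phases defined by response, so no comparison with placebo between the randomised groups is planned

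*SAP*

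**What the plan says.** The safety objective is comparative: "To investigate the safety and tolerability of intranasal esketamine compared with intranasal placebo" (SAP 1.1, repeating Protocol 2.1). One parameter listed under it is "Potential withdrawal or rebound symptoms or both following cessation of intranasal esketamine treatment". Protocol 3.1 plans to assess this with PWC-20 and POMS-2 in the first four weeks of the posttreatment phase.

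After the double-blind phase, subjects split. The posttreatment phase is for responders only. The DB follow-up phase is for "Non-Responders or subjects who withdraw from DB induction phase" (SAP 2.1). The analysis sets follow the split:

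- FU (DB): "All subjects who do not respond at the end of DB induction phase and enter the DB follow-up phase" (SAP 2.4.4).
- Safety (responders): treated subjects "who are responders at the end of the double-blind induction phase and entered the posttreatment phase" (SAP 2.4.3).

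SAP 5 adds: "Safety summaries for the follow-up phases will be based on the follow-up analysis sets described in Section 2.4.4". It names no set for the posttreatment phase; that Safety (responders) applies there is an inference from its definition.

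SAP 5.5.6 presents "The proportion of subjects with withdrawal symptoms at the end of induction phases (DB and OL) or during the DB follow-up phase, PT phase", plus open-label follow-up, with change categories against the last induction assessment. Adverse events (SAP 5.1), C-SSRS shifts (5.5.1) and POMS-2 (5.5.7) are also organised by phase. Protocol 11.8 asks for these scales to be summarised descriptively by visit and treatment group. The one scheduled PWC-20 that covers every arm together is described this way: "The PWC-20 will be performed for all subjects on Day 25 DB and Day 25 OL to establish a baseline prior to discontinuation".

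**The concern.** Response at Day 28 is a post-randomisation outcome, and the trial is sized on the expectation that esketamine changes it: Protocol 11.2 assumes MADRS differences of 4 to 5 points. If the drug works, responders on esketamine include people who would not have responded on placebo. The two arms then hold different kinds of patient within the posttreatment phase, and also within follow-up. A by-arm table inside either phase no longer compares randomised groups.

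At stake is a stated secondary objective. A reader of the clinical study report will look for withdrawal symptoms on esketamine against placebo and find two tables, each conditioned on response and each small.

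**Working it through.** **1. Where each measure has an all-arm result after the last double-blind dose (Day 25)**

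| Measure | All-arm result after Day 25 | Later results |
|---|---|---|
| PWC-20 | none scheduled (Day 25 is predose) | by phase |
| POMS-2 | none (SAP 5.5.7 summarises the PT and follow-up phases only) | by phase |
| C-SSRS | Day 28 (SAP Table 1) | by phase |
| Adverse events | to the DB end date, about Day 28 (SAP 2.1.2, 5.1) | by phase |

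The open-label phases have no placebo group. No table covering both post-cessation phases is specified.

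**2. Whether the data would allow one**

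Posttreatment days count from DB Day 1. Follow-up days count from the day after DB end (SAP 2.1.2, 2.1.3, Table 1). For a completer with DB end on Day 28, days since the last dose are:

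- Posttreatment, day − 25: Days 32, 39, 46 and 53 give 7, 14, 21 and 28.
- Follow-up, 28 + k − 25: F7, F14 and F28 give 10, 17 and 31.

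PWC-20 is scheduled at all of these visits; POMS-2 at all except Day 46. The streams differ by about 3 days, and F28 falls outside a strict 28-day window.

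**3. Arm sizes**

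Protocol 11.2: 72 + 3 × 37 = 183. With 12.5% dropout, 63/0.875 = 72 and 32/0.875 = 36.6, rounded to 37. A Dunnett calculation with 63 and 32 evaluable gives 79.4% any-dose power, in line with the stated 80%. The point itself rests on no figure in the plan.

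**4. Illustration with no withdrawal effect**

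Assumed, because the documents give no response or symptom rates: 20% of subjects respond on either treatment, 20% only on esketamine, 60% on neither. New or worsened symptoms occur in 10%, 20% and 30% of these types.

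- Responders: placebo 10%; esketamine (0.2 × 0.10 + 0.2 × 0.20)/0.4 = 15%.
- Nonresponders: placebo (0.2 × 0.20 + 0.6 × 0.30)/0.8 = 27.5%; esketamine 30%.
- Everyone: 0.2 × 0.10 + 0.2 × 0.20 + 0.6 × 0.30 = 24% in both arms.

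Standard error of a difference for one dose against placebo, at a 20% rate and without dropout, is √[0.16(1/n₀ + 1/n₁)]:

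- Responders (14.4 and 14.8): 14.8 points.
- Nonresponders (57.6 and 22.2): 10.0 points.
- Pooled (72 and 37): 8.1 points.

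The spurious gaps are 5/14.8 = 0.34 and 2.5/10.0 = 0.25 of a standard error.

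**5. A second model**

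One latent factor raises the chance of response and lowers the chance of symptoms (loadings 0.5 to 0.9). Assumed response is 15–30% on placebo and 30–50% on esketamine; assumed symptom rate is 30%. With no true effect, the difference is 0 overall, +1.3 to +4.8 points in responders and +2.0 to +12.5 in nonresponders.

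The 95% half-widths, 1.96√[0.21(1/n₀ + 1/n₁)], are about 18 points for all randomised subjects, 28–38 in responders and 21–24 in nonresponders. The largest gap, 12.5 points, arises where the half-width is 24.4, a standard error of 24.4/1.96 = 12.4. It is therefore about one standard error, under the strongest association assumed.

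**The case against.** A reader might infer that no post-dose comparison of the arms exists for any measure. The documents do not support that. C-SSRS at Day 28 and treatment-emergent events up to DB end are available in all arms about three days after the last dose. Protocol 1.1.2.1 gives a mean terminal half-life of 5.86 to 9.83 hours, so 72 hours is at least 72/9.83 = 7.3 half-lives. This stands, but the window is short and contains no scheduled PWC-20.

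It can also be said that completers who continue enter only one of two exclusive phases, so a reader could add the two tables. That works only partly. Subject-level results such as any new or worsened symptom cannot be rebuilt from visit counts on different clocks. The place of early withdrawals is also unclear, because the FU (DB) wording leaves them out while the phase definition includes them. At the planned 12.5% dropout this affects up to 0.125 × 183 ≈ 23 subjects.

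The summaries are descriptive, with no test or decision rule, and reporting by phase follows the protocol. The rates in the illustrations are assumed, and both models show only a false excess on esketamine; a masked real effect has not been calculated. All of this stands and limits the weight of the point. Pooling also mixes different background care: the oral antidepressant stays stable in the posttreatment phase, while follow-up allows standard of care and lifts most of the prohibited-medication list.

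**Conclusion.** The point holds in a limited form. For PWC-20 and POMS-2, and for adverse events and C-SSRS beyond about Day 28, the plan has no four-week post-cessation comparison of esketamine with placebo between randomised groups, although the objective is worded as one. That follows from the phase and analysis-set definitions and needs no assumed rate.

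The size of any distortion does rest on assumptions. Across the two models it ranges from about 1 to 12.5 points, mostly well under one standard error and at most about one. A reader might go further and conclude that the tables will show a false withdrawal signal, or that the comparison has been lost. Neither follows: direction and size are unknown, and the visits needed are already scheduled. This is a cheap improvement to a descriptive secondary safety analysis and does not touch the primary result.

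**What to change.** Add to SAP 5.5.6, and to the adverse event, C-SSRS and POMS-2 sections, one descriptive summary by randomised arm of all Safety (DB) subjects with a post-cessation assessment, early double-blind withdrawals included.

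- **Timing.** Use windows in days since the last double-blind dose, not visit labels, wide enough to hold F28: for example about 4–14, 15–24 and 25–35 days. POMS-2 has no Day 46 visit, so its first cut should fall between 10 and 14 days, which pairs Day 39 (14 days) with F14 (17 days). For early withdrawals, the early-withdrawal visit may come 7 days after discontinuation and extends DB end, so F28 can fall 7 + 28 = 35 days or more after it; the upper limit should allow for this. Censor at the first open-label dose.
- **PWC-20.** Report new or worsened symptoms against the last on-treatment assessment, by window and at any time. Take one assessment per window, because the posttreatment phase offers four visits and follow-up three. Subjects who leave before Day 25 have no scheduled on-treatment PWC-20; report their symptoms as present or absent.
- **Definitions.** Reconcile FU (DB) in SAP 2.4.4 with the DB follow-up phase in SAP 2.1 so that early withdrawals are counted, and name the set used for posttreatment safety.
- **By-phase tables.** Keep them as supportive.

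The cost is SAP wording and a few tables, with no new visits. State as limitations that timing differs by about 3 days between the two streams (more for early withdrawals) and that background care differs between the phases.

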Visit number	1.1 ^b	2.1 ^b	2.2	2.3	3.1 ^a	3.2	3.3	3.4	3.5	3.6	3.7	3.8	3.9	3.10 ^m	EW ^c	
Study Week	Within 4 weeks of Day P1	-6	-4	-2	1			2		3		4			—	
Study day	-70 (P-28 to P-1)	-42 (P1)	-28 (P15)	-14 (P29)	1 (P43) Prerandomization Postrandomization		2	4	8	11	15	18	22	25	28	EW
Clinic visit window (days)		-3	±3	±3	—	—	—	±1	±1	±1	±1	±1	±1	±1	±1	—
Remote MADRS interview window (in days; relative to Study day [not including visit window])		-3	±3	±3	—	—	—	—	-2 ^d	—	-2 ^d	—	-2 ^d	—	-2 ^{d,p}	—
Clinic visit (C) or remote MADRS interview only (RM)		C	C	C	C		RM	C	C	C	C	C	C	C	C	C
Ongoing Subject Review																
Concomitant therapy	X	X	X	X	X	X		X	X	X	X	X	X	X	X	X
Adverse events	X	X	X	X	X	X		X	X	X	X	X	X	X	X	X

Footnotes:

Note: On intranasal dosing days, time 0 is defined as the time of the first intranasal spray. Therefore, postdose time points are referenced from this.

- Visit 3.1 Prerandomization must coincide exactly on the same day as Visit 3.1 Postrandomization. All subjects who will be randomized and enrolled in the double-blind induction phase must meet all of the inclusion criteria and none of the exclusion criteria at Visit 3.1 Prerandomization. After randomization, all subjects will proceed to Visit 3.1 Postrandomization.
- If clinically indicated, cross tapering is allowed.
- If a subject withdraws before the end of the double-blind induction phase (ie, before completing Visit 3.10/Day 28) for reasons other than withdrawal of consent, an EW Visit should be conducted within 1 week of the date of discontinuation, followed by the follow-up phase. If the EW Visit is conducted on the same day as a scheduled visit, duplicate assessments are not required.
- MADRS assessment should be conducted at predose.
- Predose (if/when performed on intranasal dosing days). With the exception of postdose assessments, subject-reported outcome assessments should be administered before all other study-related procedures during a clinic visit.
- Postdose vital signs will be performed at 40 minutes, 1 hour, and 1.5 hours postdose. Please refer to Section 6.3.1 for guidance for blood pressure monitoring on intranasal dosing days.

-
- g. Twelve-lead ECG will be performed at $t=1$ hour postdose at Visit 3.1 Postrandomization. Twelve-lead ECG will be performed at $t=1$ hour postdose at Visits 3.4 to 3.9 (only at the time points indicated), but no predose ECGs are required at Visits 3.4 to 3.9. A time window of ± 15 minutes is permitted.

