The PWC-20 is a 20-item simple and accurate method to assess potential development of discontinuation symptoms after stopping of study drug. The PWC-20 is a reliable and sensitive instrument for the assessment of discontinuation symptoms.⁵⁵ Discontinuation symptoms occur early and disappear rather swiftly, depending upon speed of taper, daily medication dose, and drug elimination half-life.

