| | | OL F/U 14 | Week 2 (OL F/U) | 11-21 | 14 |
| | | OL F/U 28 | Week 4 (OL F/U) | 22 to end of OL F/U | 28 |
| OL F/U final visit | | End Point (OL F/U) | 1 to end of OL F/U | | |
| MOAA/S ^c Oxygen Saturation ^d (predose and every 15 minutes to 1.5H) BPRS+ and CADSS (predose, 40M, 1.5H) CGADR ^e (1H, 1.5H) | DB | 1 | Baseline (DB) | ≤1 | 1 |
| | | 4 | Day 4 (DB) | 2-6 | 4 |
| | | 8 | Day 8 (DB) | 7-9 | 8 |
| | | 11 | Day 11 (DB) | 10-13 | 11 |
| | | 15 | Day 15 (DB) | 14-16 | 15 |
| | | 18 | Day 18 (DB) | 17-20 | 18 |
| | | 22 | Day 22 (DB) | 21-23 | 22 |
| | | 25 | Day 25 (DB) | 24 to end of DB | 25 |
| | | DB final visit | End Point (DB) | 2 to end of DB | |
| | OL | OL 1 | Baseline (OL) | ≤1 (predose) | 1 |
| | | OL 4 | Day 4 (OL) | 2-6 | 4 |
| | | OL 8 | Day 8 (OL) | 7-9 | 8 |
| | | OL 11 | Day 11 (OL) | 10-13 | 11 |
| | | OL 15 | Day 15 (OL) | 14-16 | 15 |
| | | OL 18 | Day 18 (OL) | 17-20 | 18 |
| | | OL 22 | Day 22 (OL) | 21-23 | 22 |
| | | OL 25 | Day 25 (OL) | 24 to end of OL | 25 |
| | | OL final visit | End Point (OL) | 2 to end of OL | |
| PWC-20 | DB | 25 | Day 25 (DB) | 2 to end of DB | 25 |
| | | DB F/U | DB F/U 7 | Week 1 (DB F/U) | DB F/U start day-10 |
| | DB F/U | DB F/U 14 | Week 2 (DB F/U) | 11-21 | 14 |
| | | DB F/U 28 | Week 4 (DB F/U) | 22 to end of DB F/U | 28 |
| | | DB F/U final visit | End Point (DB F/U) | 1 to end of DB F/U | |
| | PT | 32 | Week 1 (PT) | PT start day to 35 | 32 |
| | | 39 | Week 2 (PT) | 36-42 | 39 |
| | | 46 | Week 3 (PT) | 43-49 | 46 |
| | | 53 | Week 4 (PT) | 50-60 | 53 |
| | | 67 | Week 6 (PT) | 61-74 | 67 |
| | | 81 | Week 8 (PT) | 75-95 | 81 |
| | OL | OL 25 | Day 25 (OL) | 2 to end of OL | 25 |
| | OL FU | OL F/U 7 | Week 1 (OL F/U) | OL FU start day-10 | 7 |
| | | OL F/U 14 | Week 2 (OL F/U) | 11-21 | 14 |
| | | OL F/U 28 | Week 4 (OL F/U) | 22 to end of OL F/U | 28 |
| OL F/U final visit | | End Point (OL F/U) | 1 to end of OL F/U | | |
| Pharmacokinetics | DB | 4 | Day 4 (DB) | 2-6 | 4 |
| | | 25 | Day 25 (DB) | 24 to end of DB | 25 |
| | OL | OL 25 | Day 25 (OL) | 24 to end of OL | 25 |

^a For DB and posttreatment phases, the time interval is relative to the first day of DB phase. For other phases, the time interval is relative to the first day of that phase.

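### For subjects who stop before Day 25 (or OL25), the PWC-20 reference is an early-withdrawal assessment that can fall well after the last dose, so the change categories can understate withdrawal symptoms

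*SAP*

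**What the plan says.** - **Purpose (SAP 5.5.6).** "The PWC-20 will be performed for all subjects on Day 25 DB and Day 25 OL to establish a baseline prior to discontinuation".
- **Rule (SAP 5.5.6).** "symptoms at PT phase and follow-up phases will be compared to the last assessment in the relevant induction phase (DB and OL"; nothing requires that assessment to be on treatment. The results are sorted into "new or worsened symptoms, symptoms present and unchanged, no symptoms, and improved".
- **Schedule (Protocol, Time and Events Schedules 1 and 3).** The only induction-phase PWC-20 assessments are at Day 25 (Visit 3.9) or OL25 (Visit 5.9), both predose, and in the EW column.
- **EW timing (footnote c of Schedule 1, footnote a of Schedule 3).** For a subject who leaves the phase early "for reasons other than withdrawal of consent, an EW Visit should be conducted within 1 week of the date of discontinuation"; the follow-up phase comes after it.
- **Phase dates (SAP 2.1.2).** The double-blind (DB) phase ends on the later of the last DB visit and the completion or withdrawal date, and follow-up starts the next day. The open-label (OL) phase uses the same rule.
- **Analysis window (SAP 2.3, Table 1).** "PWC-20 | DB | 25 | Day 25 (DB) | 2 to end of DB | 25". This is the single DB slot for the scale.
- **Expected course (Protocol 9.6).** "Discontinuation symptoms occur early and disappear rather swiftly", depending on taper speed, dose and elimination half-life.

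**The concern.** The aim and the operative rule agree for completers but not for subjects who stop early. Anyone who stops before Day 25 has no PWC-20 from the dosing period. The EW value is the only induction-phase record, it carries the Day 25 label, and it becomes the reference. If EW takes place after symptoms have begun, those symptoms sit in the baseline. Their persistence is then read as no change and their fading as improvement.

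Withdrawal or rebound symptoms after cessation are a named secondary safety objective (Protocol 2.1). The error runs in one direction, toward no withdrawal effect.

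**Working it through.** The plan gives no figure to reproduce here. The check traces the dates, then the classification, then the numbers.

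**1. Where EW falls.** An EW visit held after the withdrawal date is the last visit of the induction phase, so by SAP 2.1.2 it sets the phase end. It then lies inside the Table 1 window and before follow-up begins. For a subject who stops before Day 25 it is the only candidate for the reference.

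**2. The same interval off drug, treated in two ways.**
- A responder who completes has a PWC-20 on Day 32. That is 32 − 25 = 7 days after the last scheduled dose, and it is scored as an outcome (Week 1 of the posttreatment phase).
- An early withdrawer seen at EW 7 days after the last dose has that PWC-20 scored as the reference. Follow-up days count from the start of that phase (Table 1, footnote a), so F7 comes about 7 + 7 = 14 days after the last dose.

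**3. How late EW can be.** Sessions are on Days 1, 4, 8, 11, 15, 18, 22 and 25, so 3 to 4 days apart. If discontinuation is dated at the next planned session (an assumption), EW can be up to 3 + 7 = 10 or 4 + 7 = 11 days after the last dose.

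**4. Half-lives off drug.** Protocol 1.1.2.1 gives mean terminal half-lives of 5.86 to 9.83 h for intranasal esketamine in healthy subjects.
- Completer's Day 25 predose reference, 3 days after Day 22: 72/9.83 = 7.3 to 72/5.86 = 12.3 half-lives.
- EW 7 days after the last dose: 168/9.83 = 17.1 to 168/5.86 = 28.7 half-lives.

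Both references are many half-lives after a dose. What separates them is whether the assessment falls inside or beyond the normal dosing interval.

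**5. Classification.** Take a subject with symptom level 0 on drug and 2 at EW (illustrative levels):

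| Follow-up level | Against EW (current rule) | Against an on-drug reference |
|---|---|---|
| 0 | improved | no symptoms |
| 1 | improved | new or worsened |
| 2 | present and unchanged | new or worsened |
| 3 | new or worsened | new or worsened |

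The rule misclassifies symptoms that persist or ease. It still catches those that worsen after EW.

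**6. How many.** Protocol 11.2 assumes 12.5% drop-out with 72 placebo and 3 × 37 = 111 esketamine subjects. If every drop-out is a DB withdrawal before Day 25 with an EW visit:
- all arms: 0.125 × 183 = 22.9
- placebo: 0.125 × 72 = 9.0
- esketamine: 0.125 × 111 = 13.9, or 0.125 × 37 = 4.6 per dose arm

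**The case against.** **The half-life argument is weaker than it looks.** A reader might infer from 17 to 29 half-lives that every EW assessment differs in kind from the completers' reference. The completers' own reference is 7 to 12 half-lives off drug, and EW may coincide with a scheduled visit. An EW visit within 3 to 4 days of the last dose is therefore comparable. This stands, and it confines the problem to later EW visits, whose frequency the documents do not give.

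**The count is a ceiling.** A reader might infer that 23 subjects will be misclassified. The 12.5% is a planning assumption, about 9 of the 23 would be on placebo, and subjects who withdraw consent have no EW visit. A doubtful reference also misleads only if symptoms arose between stopping and EW and then persisted or eased. This stands.

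**The objective does not rest on these categories alone.** SAP 5.5.6 also reports the proportion with symptoms at the end of induction and in each later phase, and withdrawal terms appear among the adverse events of special interest (SAP 5.1). No test depends on the table. This stands, except that EW symptoms appear in the raw proportions as end-of-induction symptoms and not as post-cessation ones.

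**The size of any effect is unknown.** The Protocol 9.6 text is general to the instrument, and Protocol 1.1.2.3 says that no specific ketamine withdrawal syndrome has been described. This limits what can be said about magnitude but does not make the reference right.

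**The text is ambiguous in places.** SAP 2.1 puts DB withdrawers in the DB follow-up phase, but FU (DB) in SAP 2.4.4 is worded around non-response at the end of induction, so they may or may not enter the table. FU (OL) clearly includes OL withdrawers. For a subject who stops after a Day 25 assessment, the closest-to-target rule in SAP 2.3 favours Day 25, while the last-assessment rule in 5.5.6 favours EW. SAP 5.5.6 and Table 1 do not name the EW visit; if it belonged to follow-up, these subjects would have no reference. Each reading needs clarifying, and none supplies an on-treatment reference for those who stop before Day 25.

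**Conclusion.** The point holds in limited form. For subjects who stop intranasal drug before Day 25 or OL25, the stated rule uses an EW value as the reference, contrary to the section's own aim. Where EW falls beyond the usual 3-4 day dosing interval, the change categories are biased toward no withdrawal effect for symptoms that persist or ease.

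At most about 23 of 183 DB subjects, about 14 on esketamine, would have a questionable reference. The number falls with consent withdrawals and early EW visits. OL early withdrawers are affected in the same way; the plan gives no number for them. This rests on the 12.5% drop-out assumption and on EW counting as an induction-phase visit, which follows from the schedules and SAP 2.1.2.

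Completers are unaffected. The documents do not support inferring that the withdrawal objective is invalidated or that esketamine withdrawal symptoms are being hidden. The fault lies in a descriptive safety table and should be corrected because correction is cheap.

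**What to change.** - In SAP 5.5.6 and Table 1, define the reference as a PWC-20 taken predose on a dosing day (Day 25 or OL25), and state that a later EW value does not replace it.
- Label EW PWC-20 values as post-cessation and show days since last dose.
- Do not pool subjects without an on-treatment PWC-20 in the change categories. Report them in a separate table with symptom presence at EW, F7, F14 and F28 and any worsening after EW. Excluding them outright would lose those who worsen after EW, whom the current rule does capture.
- Reconcile FU (DB) in SAP 2.4.4 with the phase definition in 2.1, so that it is clear early withdrawers are included.

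The cost is SAP wording, one extra table and a smaller denominator in the main change table. No new data are needed. The change cannot create an on-drug reference for subjects who stopped before Day 25, because none was scheduled; it only stops a post-cessation value from serving as one.
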